## 1. Introduction

This document describes the rules and conventions to be used in the presentation and analysis of efficacy and safety data for protocol 093-050. It describes, in detail, the data and endpoints to be summarized and analyzed, including specifics of the statistical analyses to be performed.

This Statistical Analysis and Reporting Plan (SAP) is based on protocol version 6.0, dated 7June2013.

## 2. Study objectives

The objective of this study is to confirm the long-term safety and maintenance of effect of eslicarbazepine acetate (flexible dose range of 800 mg to 2400 mg) in subjects with partial onset seizures, with or without secondary generalization, not well controlled by current AEDs.

### 2.1. Primary objective

To evaluate the 1-Year Open-Label Period and Post-1-Year Open-Label Period safety and tolerability of eslicarbazepine acetate flexible dosing within the range of 800 mg to 2400 mg in subjects with partial epilepsy who have participated in an 18-week double-blind eslicarbazepine acetate monotherapy study (Protocols 093-045 or 093-046).

### 2.2. Secondary objectives

- To evaluate the maintenance of the therapeutic effects of eslicarbazepine acetate over a 1-Year Open-Label Period and Post-1-Year Open-Label Period.
- To evaluate the health-related quality-of-life, suicidality, and depressive symptoms over a 1-Year Open-Label Period and Post-1-Year Open-Label Period.

## 3. Study design

### 3.1. General Description

This study is a long-term, multicenter, open-label, safety extension study in male and female subjects (aged 16 to 70 years, inclusive) with partial onset seizures who have just completed, discontinued, or exited the 18-week treatment phase of Protocols 093-045 or 093-046. The initial study duration is 1-Year Open-Label Period with the option of continuing study drug treatment Post-1-Year Open-Label Period until a subject discontinues study, the study drug becomes clinically available in the subject's locale, or the sponsor terminates the study drug clinical development program.

This study will evaluate the safety and maintenance of effect of long-term eslicarbazepine acetate treatment at flexible doses in the range of 800 mg to 2400 mg once-a-day (QD) over a 1-Year Open-Label Period and a Post-1-Year Open-Label Period.

[figure not shown]
Subjects who enter the present study will receive a starting dose of 1600 mg QD of eslicarbazepine acetate, orally for 1 week at the start of the 1-Year Open-Label Period. The starting dose for subjects who had a dose reduction during participation in studies 093-045 or 093-046 will be 1200 mg and not 1600 mg. At the end of this 1-week period, subjects will be allowed to continue at this dose or at the discretion of the Investigator, increase, or decrease dose as necessary for efficacy or tolerability reasons. There is no limit on the number of dose increments or reductions during the study, however, all dose increases or reductions should occur in steps of 400 mg and a minimum of 1 week must pass between one dose change and the next. Dose reductions of more than 400 mg are allowed at the discretion of the Investigator for a documented safety reason. The maximum allowed dose of eslicarbazepine acetate is 2400 mg QD and the minimum allowed dose is 800 mg QD in this study. Subjects who continue into the Post-1-Year Open-Label Period part of the study will continue to receive the same dose of study drug that they received at Visit 7 (end of 1-Year Open-Label Period of treatment). The same dosing rules as in the 1-Year Open-Label Period part of the study are applicable in the Post-1-Year Open-Label Period part. Subjects with a clinically significant increase in seizure frequency, duration, or severity, who have not responded to or did not tolerate an increase in dose of study drug, may be started on an additional antiepileptic drug (AED) during both the 1-Year Open-Label Period and Post-1-Year Open-Label Period parts of the study. A maximum of two additional AEDs to control seizures will be allowed, however oxcarbazepine will not be allowed. If, after the addition of the second additional AED, the subject experiences an adverse event, the dose of eslicarbazepine acetate should be reduced before changing the dose of the concomitant AED. In addition, for subjects with a vagal nerve stimulator (VNS), the device setting may be changed as needed.

Subjects who require doses outside of the 800 mg QD to 2400 mg QD range or more than 2 additional AEDs during the 1-Year Open-Label Period or Post-1-Year Open-Label Period parts of the study will be discontinued from study participation.

Physicians may prescribe lorazepam for rescue use. Diazepam (rectal gel) as an emergency medication will be provided by the sponsor (via prescription from local physician). In countries where lorazepam and/or diazepam rectal gel are not available, alternate treatments are allowed per Appendices XII and XIII in the protocol.

### 3.2. Study Schematic

EOS=end of study; ET=early termination; M=month; V=visit.

\*Corresponds to Visit 9 in Protocols 093-045 and 093-046. \*\*1200 mg QD for subjects who had a dose reduction while participating in Protocols 093-045 or 093-046.

### 3.3. Determination of Sample Size

Subjects will continue on to this study from Protocols 093-045 or 093-046 as of their own choosing. Therefore, the sample size is outside of statistical considerations.

## 4. Changes in the Conduct of the Study or Planned Analysis

### 4.1. Changes in the Conduct of the Study

Six amendments have been incorporated into protocol 093-050 since final protocol.

### 4.2. Changes from Analyses Planned in the Protocol

The following change was made to the analysis planned in the protocol. This change was made prior to finalization of the SAP and prior to database lock.

The protocol in Section 7.2.3 indicates that the fraction of subjects who completed treatment at each visit post-1-year will be summarized. The change to this endpoint is that the fraction of subjects who completed treatment only for the entire post-1-year period will be summarized.

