Abbreviations: A=Electronic Data Capture (Inform); B=Laboratory Information Management System (LIMS); C=Core Lab Over-Read; C-SSRS=Columbia Suicidality Severity Rating Scale; EOS=End of Study; ET=Early Termination; MADRS=Montgomery-Asberg Depression Rating Scale; NTx=N-telopeptides of type I collagen cross-links; SCN=Screening; 25-OHD=25-hydroxyvitamin D; TSH=thyroid stimulating hormone; PGI=Patient Global Impression; PTH=parathyroid hormone; QOLIE-31=31-Item Quality of Life in Epilepsy.

- a. Demographic information, medical history, psychiatric history, medication history, magnetic resonance imaging/computerized tomography scans, electroencephalogram data, HLA-B\*1502 genotyping, and Hepatitis B/C screen results collected during the screening visit of Protocols 093-045 or 093-046 will apply for this study as well.
- b. Clinic visits to occur at intervals of 3 months during the post-1-year part.
- c. Letters in this column identify the computerized systems that will be used in this protocol (Appendix IX in protocol).
- d. The symbol “•” represents procedures performed at Visit 9 of Protocols 093-045 or 093-046, the results of which will apply to Visit 1 of the present study as well. These procedures do not have to be repeated.
- e. In street clothes without shoes and jacket/coat.
- f. Fasting labs.
- g. These assessments are not required to be performed if this visit falls in the post-1-year part of the study.
- h. If this visit falls in the post-1-year part of the study, this assessment may be performed only if clinically indicated (per Investigator judgement on a previously noted abnormality).
- i. Includes serum 25-OHD, PTH, osteocalcin, bone-specific alkaline phosphatase, and urinary NTx.
- j. At Visit 5 only.
- k. Every 6 months (i.e. Visits 7, 9, 11, 13, etc.).
- l. Only in subjects ≥18 years at time of signing informed consent in Protocols 093-045 or 093-046.
- m. Only for subjects who discontinue study during the post-1-year part of study.
- n. Fill out “since last visit” scale (Appendix VII in protocol).
- o. Only for subjects who discontinue study during the 1-year part of study.
- p. Only for subjects who continue into the post-1-year part of the study.

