## **2 Completion rates**

Completion rates for Post- 1-Year Open-Label Period will be defined as the proportion of subjects from the ITT population who had the reason for withdrawal from the Post- 1 Year Open-Label Period either “Sponsor terminates clinical study” or “Study drug became available in subject’s locale” from the end of study page in the CRF.

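### The Post-1-Year completion rate has no fixed time base and mixes retention with length of follow-up; the planned Kaplan-Meier retention analysis should report fixed-time estimates from Visit 7

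*SAP*

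**What the plan says.** SAP section 4.2 reports that protocol section 7.2.3 planned that "the fraction of subjects who completed treatment at each visit post-1-year will be summarized", and replaces this with a single figure: "the fraction of subjects who completed treatment only for the entire post-1-year period will be summarized". On timing it says: "This change was made prior to finalization of the SAP and prior to database lock". It gives no reason for the change.

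Section 3.1 lets treatment after Year 1 run "until a subject discontinues study, the study drug becomes clinically available in the subject's locale", or until "the sponsor terminates the study drug clinical development program". The footnotes to the schedule in section 5.1 add: "Clinic visits to occur at intervals of 3 months during the post-1-year part".

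Section 5.2.3, item 2, takes as completers the ITT subjects whose end-of-study reason was "either “Sponsor terminates clinical study” or “Study drug became available in subject’s locale". No minimum time on drug is required. Section 7.6 reports the result as a proportion with a binomial 95% CI, under the same heading as the Year-1 completion rate, which section 5.2.2 defines over Visit 1 to Visit 7.

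The SAP also plans a Post-1-Year retention time (section 5.2.3, item 4; section 7.6, Treatment retention). This is a Kaplan-Meier median with 95% CI, timed from the first monotherapy dose in the parent study. Sponsor termination and local availability are censored.

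**The concern.** Under this definition, a subject whose country gets the drug three months after Visit 7 is a completer. A subject who stays four years and then leaves is not. The proportion therefore depends on how long each subject could have been followed, which is set by enrolment date and local availability, as well as on how many stopped treatment.

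Maintenance of effect after Year 1 is a secondary objective (section 2.2), and the seizure diary stops at Visit 7 (section 5.2.1). No seizure-based result exists after that. The endpoints specific to the later period are the PGI, completion, time on monotherapy and retention time. A reader looking for long-term retention will turn to the completion rate, and may compare it with the Year-1 rate printed beside it.

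**Working it through.** The documents give no expected completion or discontinuation rate for this period, so there is no planned figure to reproduce. The rates and closure times below are assumptions, used only to show how the measure behaves.

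**Set-up.** Let q be the yearly discontinuation for non-administrative reasons, taken as constant, and T the years from Visit 7 to the administrative end. Among entrants, crude completion = (1 − q)^T.

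**1. Same retention, different closure time.**

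| q | T = 0.5 | T = 1 | T = 3 | T = 5 |
|---|---|---|---|---|
| 10% | 95% | 90% | 73% | 59% |
| 15% | 92% | 85% | 61% | 44% |
| 20% | 89% | 80% | 51% | 33% |

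For example, 0.85^0.5 = 0.92 and 0.85^5 = 0.44.

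**2. Different retention, same figure.** With q = 10% and T = 5, completion is 0.90^5 = 59%. With q = 30%, the same 59% arises at T = ln(0.590)/ln(0.70) = 1.48 years. Retention cannot be recovered from the proportion unless follow-up time is known.

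**3. The figure still responds to retention.** At T = 3 it is 86%, 73%, 51% and 34% for q = 5%, 10%, 20% and 30%.

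**4. Denominator.** These values are for entrants. The SAP divides by ITT, which is everyone who took open-label drug (section 7.1), so the reported rate is s × (1 − q)^T, where s is the share of ITT subjects entering the period. With q = 20% and T = 3, the 51% becomes 26% at s = 50% and 46% at s = 90%. The table therefore shows sensitivity to T and does not forecast what the SAP will report.

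**5. What the planned Kaplan-Meier analysis leaves open.**
- *Median only.* If q is treated as the event rate, the median falls ln 2 / −ln(1 − q) years after Visit 7. That is 4.3 years at 15% and 6.6 years at 10%, and it may not be reached.
- *Clock.* Time starts at parent-study Visit 6/Week 8. A subject who completed the 18-week parent treatment phase has 18 − 8 = 10 weeks there, and every entrant must then finish the 12 months to Visit 7. Entrants cannot have an event in this stretch of about 1.2 years (62/52 weeks). No delayed-entry handling is stated. If the analysis is run on entrants without it, the 4.3-year median would read as about 5.5 years.

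**6. Would the by-visit fraction alone be enough?** Take q = 20% and T uniform on 1 to 4 years. At 2 years, 0.80² = 64% have not discontinued, but only (4 − 2)/(4 − 1) = 2/3 have not yet reached an administrative end. The raw on-drug fraction is 0.64 × 2/3 = 42.7%, against retention of 64%.

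**7. After the fix.** Retention at a fixed time with administrative ends censored depends on q alone. It is 90%, 80% and 70% at one year, and 81%, 64% and 49% at two years, for q = 10%, 20% and 30%.

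**The case against.** The strongest reply is that the SAP already separates the two ideas. Completion is a disposition-type count. Retention is a Kaplan-Meier analysis that censors the administrative ends, as it should. Section 7.2 tabulates Post-1-Year discontinuations with reasons, section 7.5 gives exposure duration, and section 7.6 adds Kaplan-Meier time on monotherapy. The study is an open-label safety extension with no statistical sample sizing, and the change is disclosed as made before database lock. All of this stands, and it is why the point is minor. It does not supply retention at any fixed time after Visit 7, and the exposure categories stop at more than 104 weeks.

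A reader might go further than the documents allow in four ways.
- *That the rate reflects entry date and availability instead of retention.* It does not: the rate falls as discontinuation rises (step 3). It is confounded by follow-up length, not unrelated to retention.
- *That section 4.2 caused the problem and restoring the protocol's endpoint would cure it.* Step 6 shows that a raw by-visit fraction has the same fault unless administrative ends are handled. Protocol section 7.2.3 is known here only through the SAP's one-sentence description, so its definition and denominator cannot be judged.
- *That the SAP plans to compare the two periods, or countries, on completion.* It plans neither. The risk lies in how the figures will be read.
- *That the change was made with results in view.* The SAP states that it came before database lock, and nothing in the documents points the other way.

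**Conclusion.** The point holds as a limited one. The Post-1-Year completion rate is a crude proportion over a period of no fixed length, so it cannot be read as a retention rate or compared with the 12-month Year-1 rate. The Kaplan-Meier analysis handles the administrative ends but offers only a median, which may not be reached, on a clock that begins before entry to the period.

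The size is illustrative: 92% to 44% among entrants at an assumed 15% yearly discontinuation with closure at 0.5 to 5 years, and 95% to 59% at 10%. This rests on a constant rate and a common closure time, neither of which is given in the documents. No error rate, power or primary safety analysis is affected. Severity is minor: one descriptive secondary summary.

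**What to change.** Extend the Treatment retention analysis in SAP section 7.6:
- Report Kaplan-Meier retention with 95% CI at fixed times after Visit 7, for example yearly, with the number at risk at each time.
- Restrict it to subjects who entered the Post-1-Year Period, and measure time from Visit 7.
- Keep sponsor termination and local availability as censoring reasons, as now planned.
- Present the crude Post-1-Year completion count as disposition only, with follow-up time from Visit 7 beside it, and state that it is not comparable with the Year-1 completion rate.

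The cost is SAP wording and one table. The dates and end-of-study reasons are already needed for the planned retention and disposition outputs.

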## 5. Efficacy and Safety Variables

### 5.1. Schedule of Evaluations

Procedures	Visit 1/ SCN a	Visit 2	Visit 3	Visit 4	Visits 5 and 6	Visit 7	Post-1-year Visit 8 onwards	EOS/ET	Computer Systems c
	Day 0	Week 1	Mont h 1	Mont h 3	Months 6 and 9	Month 12	Month 15 onwards b		
Informed Consent	X								
Inclusion/Exclusion Criteria Review	X								A
Physical Examination	• d							X	A
Neurological Examination	•							X	A
Vital Sign Measurements	•	X	X	X	X	X	X	X	A
Height	•							X	A
Weight e	•	X	X	X	X	X	X	X	A
Clinical Laboratory Evaluation (Serum Chemistry, Hematology, and Urinalysis) f	•		X	X	X	X		X g,h	B
Coagulation Testing (PT/INR, PTT)	•		X	X	X	X		X g	B
Thyroid Panel (T 3 , T 4 , and TSH)	•		X	X	X	X		X g	B
Lipid Panel (total cholesterol, HDL-cholesterol, LDL-cholesterol, and triglycerides) f	•		X	X	X	X		X g,h	B
Bone Turnover Markers i	•				X h	X		X g	B
Serum Pregnancy Test k	•		X	X	X	X		X g	B
Urine Pregnancy Test k							X	X	
Urine Drug Screen (Central Lab)	•								B
12-Lead ECG	•		X	X	X	X		X h	C
MADRS	•				X j	X	X l	X	A
QOLIE-31 m	•				X j	X	X il	X	A
PGI Scale							X	X n	
C-SSRS o	•	X	X	X	X	X	X	X	A
Health Outcomes Assessments	•	X	X	X	X	X	X	X	A
Adverse Events	•	X	X	X	X	X	X	X	A
Concomitant Medications	•	X	X	X	X	X	X	X	A
Dispense Seizure Diary	X	X	X	X	X				
Document Seizures in Seizure Diary		X	X	X	X				A
Seizure Diary Review		X	X	X	X	X		X g	

Author:

Version Date: 19May2017

Copyright © 2010 Quintiles Transnational Corp. All rights reserved.

The contents of this document are confidential and proprietary to Quintiles Transnational Corp. Unauthorized use, disclosure or reproduction is strictly prohibited.

Procedures	Visit 1/ SCN a	Visit 2	Visit 3	Visit 4	Visits 5 and 6	Visit 7	Post-1-year Visit 8 onwards	EOS/ET	Computer Systems c
	Day 0	Week 1	Month 1	Month 3	Months 6 and 9	Month 12	Month 15 onwards b		
Dispense Study Drug	X	X	X	X	X	X p	X		A
Dispense Emergency Medication	X								
Drug Accountability		X	X	X	X	X	X	X	A
Dispense/Review MEC	X	X	X	X	X	X	X	X	

Abbreviations: A=Electronic Data Capture (Inform); B=Laboratory Information Management System (LIMS); C=Core Lab Over-Read; C-SSRS=Columbia Suicidality Severity Rating Scale; EOS=End of Study; ET=Early Termination; MADRS=Montgomery-Asberg Depression Rating Scale; NTx=N-telopeptides of type I collagen cross-links; SCN=Screening; 25-OHD=25-hydroxyvitamin D; TSH=thyroid stimulating hormone; PGI=Patient Global Impression; PTH=parathyroid hormone; QOLIE-31=31-Item Quality of Life in Epilepsy.

- a. Demographic information, medical history, psychiatric history, medication history, magnetic resonance imaging/computerized tomography scans, electroencephalogram data, HLA-B\*1502 genotyping, and Hepatitis B/C screen results collected during the screening visit of Protocols 093-045 or 093-046 will apply for this study as well.
- b. Clinic visits to occur at intervals of 3 months during the post-1-year part.
- c. Letters in this column identify the computerized systems that will be used in this protocol (Appendix IX in protocol).
- d. The symbol “•” represents procedures performed at Visit 9 of Protocols 093-045 or 093-046, the results of which will apply to Visit 1 of the present study as well. These procedures do not have to be repeated.
- e. In street clothes without shoes and jacket/coat.
- f. Fasting labs.
- g. These assessments are not required to be performed if this visit falls in the post-1-year part of the study.
- h. If this visit falls in the post-1-year part of the study, this assessment may be performed only if clinically indicated (per Investigator judgement on a previously noted abnormality).
- i. Includes serum 25-OHD, PTH, osteocalcin, bone-specific alkaline phosphatase, and urinary NTx.
- j. At Visit 5 only.
- k. Every 6 months (i.e. Visits 7, 9, 11, 13, etc.).
- l. Only in subjects ≥18 years at time of signing informed consent in Protocols 093-045 or 093-046.
- m. Only for subjects who discontinue study during the post-1-year part of study.
- n. Fill out “since last visit” scale (Appendix VII in protocol).
- o. Only for subjects who discontinue study during the 1-year part of study.
- p. Only for subjects who continue into the post-1-year part of the study.

## 5.2. Efficacy Assessment and Endpoints

### 5.2.1. Assessments

Each subject will be instructed to keep a seizure diary and record information on all seizures for the first one-year of the study starting from Visit 1 (Screening) and ending at Visit 7. Subjects or caregivers can complete the study diary; however the person who maintains the diary should remain the same throughout the study. Seizure occurrences since the previous visit, based on review of the seizure diary, will be recorded by date and seizure type on the eCRF. At return visits 2 through 7, the seizure diary will be reviewed, and collected.

The 31-Item Quality of Life in Epilepsy Scale (QOLIE-31) will be self-administered by only subjects who have completed 18 years of age at time of signing informed consent in Protocols 093-045 or 093-046.

The Montgomery-Asberg Depression Rating Scale (MADRS) measures the severity of a subject's depressive symptoms. MADRS will be performed by a credentialed and trained MADRS rater.

The Patient Global Impression (PGI) scale measures the patient impression of improvement in disease. The PGI will be subject self-administered at all visits during the Post-1-Year Open-Label Period only. The 5 individual items will be summarized with descriptive statistics for each Post-1-Year Open-Label Period visit.

### 5.2.2. 1-Year Open-Label Period Efficacy Endpoints

#### 1. Time on eslicarbazepine acetate monotherapy

Time on eslicarbazepine acetate monotherapy during 1-Year Open-Label Period will be calculated from the date of the first eslicarbazepine acetate monotherapy dose in protocol 093-045 or 093-046 (Visit 6/Week 8) to the last known dose of eslicarbazepine acetate monotherapy during 1-Year Open-Label Period as follows;

- a. For a subject who added a non-rescue AED during 1-Year Open-Label Period, Time on Monotherapy during 1-Year Open-Label Period is calculated as the date of start a non-rescue AED during 1 Year Open-Label Period minus the date of the first monotherapy dose in protocol 093-045 or 093-046.
- b. For a subject who completed the 1-Year Open-Label Period, and did not add any non-rescue AED since the date of the first monotherapy dose in protocol 093-045 or 093-046, Time on Monotherapy during 1-Year Open-Label Period is calculated as the date of the last known dose during 1-Year Open-Label Period, minus the date of the first monotherapy dose in protocol 093-045 or 093-046, plus 1.
- c. For a subject who did not complete the 1-Year Open-Label Period, and did not add any non-rescue AED since the date of the first monotherapy dose in protocol 093-045 or 093-046, Time on Monotherapy during 1-Year Open-

Label Period is calculated as the date of the known dose before the withdrawal during 1-Year Open-Label Period, minus the date of the first monotherapy dose in protocol 093-045 or 093-046, plus 1.

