## **3. Time on eslicarbazepine acetate monotherapy**

Time on eslicarbazepine acetate monotherapy during Post1-Year Open-Label Period will be calculated from the date of the first eslicarbazepine acetate monotherapy dose in protocol 093-045 or 093-046(Visit 6/Week 8) to the last known dose of eslicarbazepine acetate monotherapy during Post-1-Year Open- Label Period as follows;

- For a subject who added a non-rescue AED during Post-1-Year Open-Label Period, Time on Monotherapy during Post 1-Year Open-Label Period is calculated as the date of start a non-rescue AED during Post-1-Year Open-Label Period minus the date of the first monotherapy dose in protocol 093-045 or 093-046.
- For a subject who completed the Post-1-Year Open-Label Period, and did not add any non-rescue AED since the date of the first monotherapy dose in protocol 093-045 or 093-046, Time on Monotherapy during Post-1-Year Open-Label Period is calculated as the date of the last known dose during Post-1-Year Open-Label Period, minus the date of the first monotherapy dose in protocol 093-045 or 093-046, plus 1.
- For a subject who did not complete the Post-1Year Open-Label Period and did not add any non-rescue AED since the date of the first monotherapy dose in protocol 093-045 or 093-046, Time on Monotherapy during Post- 1-Year Open-Label Period is calculated as the date of the last known dose before the withdrawal during Post- 1-Year Open-Label Period, minus the date of the first monotherapy dose in protocol 093-045 or 093-046, plus 1.

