### **Actual Monotherapy Used subgroup**

The subjects who started on actual monotherapy (i.e. 10 weeks double-blind monotherapy from protocol 093-045 or 093-046), entered this study and did not add any non-rescue AED during the study participation will be defined as Actual Monotherapy Used subgroup.

For those subjects, the following data including ESL exposure and compliance, concomitant medication, SSF, relative (%) change from baseline in SSF, responders, TEAE, SAE, Death, TEAE leading to discontinuation, and minimum post-dose sodium level change from baseline will be summarized.

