### **Time on eslicarbazepine acetate monotherapy**

Kaplan Meier methods will be used to estimate the median time (and 95% CI) on eslicarbazepine acetate monotherapy for both 1-Year Open-Label Period and Post-1-Year Open-Label Period.

For the 1-Year Open-Label Period, time on monotherapy as defined in Section 5.2.2 will be used for analysis. Subjects who were still taking only eslicarbazepine acetate as monotherapy at the end of the 1-Year Open-Label Period of study will be censored at the last dose of the 1-Year Open-Label Period. Subjects who withdrew during the 1-Year Open-Label Period will also be censored at the time of the last known dose before the withdrawal. Subject who added a non-rescue AED will be an event on the date of the start AED during 1-Year Open-Label Period.

For the Post-1-Year Open-Label Period, time on monotherapy as defined in Section 5.2.3 will be used for analysis. Subjects who were still taking only eslicarbazepine acetate as monotherapy at the end of the Post-1-Year Open-Label Period will be censored at the last dose of the Post-1-Year Open-Label Period. Subjects who withdrew during the Post-1-Year Open-Label Period will also be censored at the time of the last known dose before the withdrawal. Subject who added a non-rescue AED will be an event on the date of the start AED during Post-1-Year Open-Label Period.

Subjects who never started the monotherapy treatment period in protocol 093-045 or 093-046 will not be included in this analysis. Change in dosage levels from protocol 093-045 or 093-046, dosage changes during protocol 093-050, and the time gap between the parent studies and the extension study will be ignored.

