#### **7.7.7 Concomitant Medication**

Other than the study drug, any medication taken by subjects during the course of the study will be considered concomitant. The number and percentage of subjects using each concomitant medication will be summarized according to the WHO Drug Class and preferred term for concomitant AED and non-AED medication separately. Subjects with multiple uses of a concomitant medication will be counted once for a given WHO Drug Class and Preferred term.

Listing of concomitant AED, non-AED medications, prior medication, and rescue and emergency medication will also be presented.

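### Time on monotherapy: a non-rescue AED started after the last eslicarbazepine dose can count as an event beyond the time on drug, and no rule ranks this against censoring for withdrawal

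*SAP*

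**What the plan says.** SAP Section 5.2.2 item 1 first defines the endpoint as running from the first monotherapy dose in the parent study "to the last known dose of eslicarbazepine acetate monotherapy during 1-Year Open-Label Period". Three rules then carry this out.

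- Rule (a) opens "For a subject who added a non-rescue AED during 1-Year Open-Label Period" and says that the time "is calculated as the date of start a non-rescue AED during 1 Year Open-Label Period minus the date of the first monotherapy dose".
- Rules (b), for completers, and (c), for non-completers, run to the last dose, plus 1. Each applies only to a subject who meets the further condition "and did not add any non-rescue AED since the date of the first monotherapy dose".

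Section 5.2.3 item 3 uses the same scheme for the post-1-year period: the time "is calculated as the date of start a non-rescue AED during Post-1-Year Open-Label Period minus the date of the first monotherapy dose".

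Section 7.6 makes the start of a non-rescue AED the Kaplan-Meier event. It also states: "Subjects who withdrew during the 1-Year Open-Label Period will also be censored at the time of the last known dose before the withdrawal". It does the same for the post-1-year period. No order is given for a subject who both withdrew and started an AED.

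The Actual Monotherapy Used subgroup in Section 6.5 is limited to subjects who started the parent monotherapy phase, entered this study and "did not add any non-rescue AED during the study participation".

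**The concern.** Rule (a) is triggered by the start of an AED and says nothing about whether eslicarbazepine is still being taken. A subject who stops the drug and begins a replacement before leaving the study meets its wording. Rule (c), which would otherwise handle the withdrawal, is closed to anyone who added an AED. Section 7.6 then offers two answers for the same subject.

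Three things are at stake.

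- **Event status.** The same clinical course, coming off the drug and being given another, is an event or censored according to when the replacement started and whether that was before exit.
- **Time.** An event dated after the last dose credits days off eslicarbazepine as monotherapy.
- **The subgroup.** Someone who stops for an adverse event and starts another AED before exit can drop out of the Actual Monotherapy Used subgroup. That subgroup reports SAEs, deaths, TEAEs leading to discontinuation and sodium change, so losing such subjects could make its safety tables look more favourable.

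Time on monotherapy is the first-listed 1-year efficacy endpoint, and its planned output is a Kaplan-Meier median with a 95% CI.

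**Working it through.** The SAP gives no event count, rate or power figure for this endpoint. Section 3.3 places the sample size outside statistical considerations. There is no stated figure to reproduce, so the check applies the rules to dated examples.

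**Can such a record arise?** The schedule in Section 5.1 collects concomitant medications at every visit through EOS/ET. Section 5.3.2 defines a concomitant medication by a lower bound only, the first dose. Section 7.7.7 says "any medication taken by subjects during the course of the study will be considered concomitant". None of these stops at the last eslicarbazepine dose. The SAP also does not say whether, for an early discontinuer, the period ends at the last dose or at the ET visit.

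**Worked subject (assumed dates).** First monotherapy dose Day 1, last eslicarbazepine dose Day 200, ET visit Day 210.

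- Rule (a): AED start minus first dose.
- Withdrawal rule: last dose minus first dose, plus 1 = 200 − 1 + 1 = 200.

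| AED starts | AED-start rule | Withdrawal rule in 7.6 |
|---|---|---|
| Day 190 (overlapping) | event at 190 − 1 = 189 | censored at 200 |
| Day 201 | event at 201 − 1 = 200 | censored at 200 |
| Day 205 | event at 205 − 1 = 204 | censored at 200 |
| Day 215 (after exit) | not triggered; rule (c) censors at 200 | censored at 200 |

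The Day 201 row changes event status only. The Day 205 row changes status and exceeds the time on drug by 204 − 200 = 4 days. The Day 190 row also meets both rules, but there monotherapy truly ended when the second drug began.

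**Illustration of sensitivity (all rates assumed).** Let A be the cumulative probability of a true AED addition and W that of withdrawal, over 70 + 365 = 435 days (10 weeks of parent monotherapy plus one year). Let q be the share of withdrawals recoded from censored to event. With independent exponential times, and ignoring the few days between last dose and AED start, the Kaplan-Meier estimate at 435 days is S = (1 − A)(1 − W)^q.

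| A, W | q = 0 | q = 0.25 | q = 0.5 | q = 1 |
|---|---|---|---|---|
| 20%, 30% | 0.80 | 0.73 | 0.67 | 0.56 |
| 20%, 40% | 0.80 | 0.70 | 0.62 | 0.48 |
| 40%, 30% | 0.60 | 0.55 | 0.50 | 0.42 |

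For example, 0.80 × 0.70^0.5 = 0.67. The median is 435 × ln 2 / (−ln S). In the second row it falls inside the 435 days only at q = 1: 435 × 0.693 / 0.734 = 411 days.

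**The case against.** The strongest reply is that the intent is clear. Adding an AED naturally means adding it to ongoing eslicarbazepine. Section 3.1 speaks throughout of additional AEDs given alongside the study drug, and the opening definition stops the clock at the last monotherapy dose. On that reading a replacement started after stopping is not an addition, rule (c) stays open, and the subgroup need not lose a pure switch. The usual time-to-event convention, whichever comes first, would also reconcile the two sentences in Section 7.6. This is plausible, but the SAP states neither the restriction nor the convention, and a literal application of rule (a) gives a different status and time.

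A second reply is that if the ET visit coincides with the last dose, the gap hardly arises. That stands as a limit on size: the documents do not show how long the gap usually is.

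A reader might also infer two stronger points, and neither is supported.

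- **That a large share of withdrawals is affected and the median shifts materially.** The documents give no rates. The illustrative q can also include AEDs that overlap eslicarbazepine, which are genuine losses of monotherapy and not part of the defect.
- **That every switch, including one begun during a taper, belongs under withdrawal censoring.** In the Day 190 example this would credit the days from 190 to 200, when two drugs were taken, as monotherapy. It would also need a judgement of why the AED was started, which is not shown to be collected.

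**Conclusion.** The point holds for AEDs started after the last eslicarbazepine dose and before study exit. For these subjects the stated rules allow either an event, at a time that can exceed time on drug, or censoring at the last dose. The event reading conflicts with the endpoint's own definition. For subjects whose AED overlaps eslicarbazepine, an event at AED start is the right result, and only the missing order of precedence needs repair.

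The size cannot be derived from the documents. The percentages above are illustrations under assumed rates, and q = 1 is an upper bound rather than an expected value. The analysis is a descriptive single-arm summary for a secondary objective with no hypothesis test, so alpha and power are unaffected. What is exposed is the Kaplan-Meier curve, its median and CI, and membership of the Actual Monotherapy Used subgroup. The correction is worth making before database lock, but it does not threaten the study's primary safety objective.

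**What to change.** In Sections 5.2.2 item 1, 5.2.3 item 3 and 7.6, state one rule:

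- A non-rescue AED started on or before the last eslicarbazepine dose is an event at the AED start, including an AED that overlaps a taper.
- Otherwise the subject is censored at the last eslicarbazepine dose.
- Time on monotherapy never runs past that dose.

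In the example, Day 190 is then an event at 189 days, and Days 201, 205 and 215 are all censored at 200.

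In Section 6.5, apply the same on-or-before-last-dose condition, so that an AED started after eslicarbazepine has stopped does not remove a subject from the subgroup.

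Report how many subjects started a non-rescue AED after the last dose. Add one sensitivity analysis that counts them as events at the last eslicarbazepine dose, because stopping the drug and being switched may not be non-informative.

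The cost is a clause in four places, one count and one extra run. It uses AED start dates and last-dose dates that the existing rules already need, and no judgement of why an AED was started.
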